### **3.5.2.2 Visits 13 and 26**

In addition to the study procedures listed for Visits 1 through 26, the following assessments will also be collected at 6 months (Visit 13) and 12 months (Visit 26) after initiating treatment with KRYSTEXXA:

- Perform swollen joint and tender joint counts
- Perform a count of the total number of palpable subcutaneous and subperiosteal tophi, if accessible

### **3.5.2.3 Visit 27: End of Study**

The final procedures at End of Study (Visit 27) (12 weeks after final KRYSTEXXA infusion) will include:

- Inquire and assess for AEs, gout flares and changes in concomitant medications since previous study visit
- Complete physical exam, reviewing same body systems as at screening visit
- Measure blood pressure, heart rate and temperature
- Collect blood samples for identification of antibodies to pegloticase or PEG
- Record SUA results obtained after the last infusion
- Instruct patients on post-study anti-hyperuricemic therapy as appropriate

### **3.5.3 Early Treatment Discontinuation Procedures**

Patients in whom KRYSTEXXA is discontinued before Visit 26 will be asked to continue in follow-up for the full duration of the study. In this case, patients are to return 4 weeks (+/- 5

days) after their final infusion of KRYSTEXXA in order to undergo early treatment discontinuation study procedures. Patients who discontinue treatment before 51 weeks (i.e., before all 26 planned KRYSTEXXA infusions) will be asked to remain in the study for follow-up assessments for the remainder of their planned treatment duration. These procedures include essentially the same procedures as Visit 26, adding only the final instruction to patients:

- Inquire and assess for AEs, gout flares and changes in concomitant medications since previous study visit
- Determine and record the reason for the early discontinuation of KRYSTEXXA
- Complete physical exam, reviewing same body systems as at screening visit
- Measure blood pressure, heart rate and temperature
- Collect blood samples for antibodies to pegloticase or PEG
- Perform swollen joint and tender joint count
- Perform a count of the total number of palpable subcutaneous and subperiosteal tophi, if accessible
- Instruct patients on post-KRYSTEXXA anti-hyperuricemic therapy as appropriate

#### Additional Follow-up Visit Procedures

The first follow-up visit will be 3 months (12 weeks) after the last KRYSTEXXA infusion, and at 3-month intervals subsequently. Follow-up visits will only be conducted for the remainder of the patient's planned 1 year of study participation. For example, subjects who discontinue treatment on or after Visit 19 would only have an Early Treatment Discontinuation Visit (at 4 weeks after discontinuation) and a 3-month post-treatment follow-up visit.)

Assessments during the post-treatment follow-up period will include:

- Inquire and assess for AEs, gout flares and changes in concurrent medications since previous study visit
- Collect blood samples for identification of antibodies to pegloticase or PEG

#### **3.5.4 Early Discontinuation from the Study**

Patients who completely discontinue their participation in the study and do not consent to be followed for the full year are to return 4 weeks (+/- 5 days) after their final infusion of KRYSTEXXA in order to undergo early discontinuation study procedures. These procedures include essentially the same procedures as Visit 26, but without SUA and adding only blood samples for antibodies and the final instruction to patients:

- Inquire and assess for AEs, gout flares and changes in concomitant medications since previous study visit
- Determine and record the reason for the early discontinuation of the patient

- Complete physical exam, reviewing same body systems as at screening visit
- Measure blood pressure, heart rate and temperature
- Collect blood samples for antibodies to pegloticase or PEG
- Perform swollen joint and tender joint count
- Perform a count of the total number of palpable subcutaneous and subperiosteal tophi, if accessible
- Instruct patients on post-study anti-hyperuricemic therapy as appropriate

### **3.5.5 Interruption of Treatment**

Dosing with KRYSTEXXA may be delayed or interrupted for example, for vacation or for intercurrent illness, without requiring a patient to be discontinued from the study. The reason for the delay or interruption will be captured in both the medical record and the CRF/eCRF. If the SUA is  $>6$  mg/dL after an interruption in treatment, the patient may still resume treatment.

### **3.5.6 Patient Discontinuation from Study**

Patients may be discontinued from the study if they withdraw consent, if they experience an AE that precludes further participation, if they are non-compliant with study procedures, if there is a protocol violation, or if treatment is discontinued due to elevation of SUA  $>6$  mg/dL. The reason for a patient not completing the study will be collected and recorded in the patient's medical record and on the CRF/eCRF. If a patient is discontinued from the study, every effort should be made to complete the procedures for an early discontinuation (see Section 3.5.4), preferably 4 weeks after their last dose of KRYSTEXXA but sooner if necessary. AEs that are possibly or probably drug-related, are of moderate or greater severity and are ongoing when a patient is discontinued or at the final visit will be followed up to 30 days, or until the event resolves or stabilizes, whichever is sooner. Follow-up may entail only a phone call, or it may require additional examinations or laboratory evaluations, depending upon the event. Documentation of the follow-up will be included in the patient's medical record and a summary will be provided to Savient or designee for possible inclusion in the clinical study report.

Patients who discontinue KRYSTEXXA, for example due to an IR or an elevation of SUA  $>6$  mg/dL, will be asked to remain in the study in follow-up for the remainder of their planned treatment duration (see Section 3.5.3). In this case, the reason for KRYSTEXXA discontinuation will be collected and recorded in the patient's medical record and on the CRF/eCRF. The medical monitor must be notified as soon as possible about any patient's discontinuation.

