### **3.4.1.2 Reference therapy**

KRYSTEXXA is commercially available in the US as a sterile, clear, colorless solution containing 8 mg/mL pegloticase in phosphate-buffered saline. KRYSTEXXA® (pegloticase) concentrations are expressed as concentrations of uricase protein. Each mL of KRYSTEXXA contains 8 mg of uricase protein conjugated to 24 mg of 10 kDa monomethoxypoly(ethylene glycol) (mPEG). Excipients include disodium hydrogen phosphate dihydrate, sodium chloride, sodium dihydrogen phosphate dihydrate and water for injection.

KRYSTEXXA is supplied in a single-use, 2 mL glass vial with a Teflon coated (latex-free) rubber injection stopper to deliver KRYSTEXXA as 8 mg of uricase protein in 1 mL volume for i.v. infusion. Before preparation for use, KRYSTEXXA should be stored in the carton, maintained under refrigeration between 2°C and 8°C (36°F and 46°F), protected from light and should not be shaken or frozen.

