#### **6.1.6 Safety Evaluation**

Adverse events will be summarized by presenting the proportion of patients having any AE, overall and by body system, and by event as defined by the MedDRA preferred term. Separate summary tables will be provided for IRs, anaphylaxis AEs, and immune complex-related AEs.

For each type of the primary safety endpoints, one event, at most, will be counted per patient. The 95% (exact) confidence interval estimates for each type of safety endpoint will be reported for the rate of incidence at the final analysis. The following hypothesis will be specifically tested: the rate of IRs seen in the Phase 3 studies will be reduced in this study by monitoring SUA prior to infusions and discontinuing therapy if levels increase to above 6 mg/dL, particularly when 2 consecutive levels above 6 mg/dL are observed. With at least 500 patients enrolled with 1 year follow-up, the power of detecting a 26% IR rate (the observed value from the pre-approval Phase 3 studies) against 13% is at least 90%. The rate of IRs reported during the study will be reported and compared descriptively to the rates observed in the pre-approval Phase 3 studies.

Descriptive statistics for laboratory values, vital signs, and their changes from baseline will be provided. Safety data will be listed as appropriate. Further details will be specified in the SAP.

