#### **Report Format/Structure**

- Enrollment
  - What has been done to address enrollment over the years?
  - o Number of patients enrolled per calendar year?
  - o Number of sites recruited for study since study initiation
    - Number of actively enrolling sites
      - Number of actively enrolling sites per calendar year
    - Number of sites dropping out per year
    - Reason for site drop outs
- Safety Endpoints
  - O Number of IRs by dose (1st v. 2nd v. 3rd etc.)
  - o IRs by severity or not by dose
  - O Number of anaphylaxis by dose (1st v. 2nd v. 3rd etc.)
  - o Anaphylaxis severity or not by dose
- Efficacy endpoints
  - o Number of patients meeting the primary efficacy effect at 24 and 52 weeks
  - o Number of protocol treated patients meeting the primary efficacy effect
- 1. Patient disposition flow chart:
  - a. Total Number of patients screened
  - b. Number of patients dosed
    - i. Number of patients currently receiving drug
  - c. Number of completers at 24 weeks
    - i. How many were responders versus non responders (based on primary efficacy criteria)
  - d. Number of completers at 52 weeks
    - i. How many were responders versus non responders (based on primary efficacy criteria)
  - e. Number of non-completers at 24 and 52 weeks
    - i. Reason for non-completing (AE, IR, etc.)
  - f. Number of patients treated per protocol through 24 and 52 weeks
    - i. Chart out responders versus non-responders in this cohort
- 2. Dosing:
  - a. Total number of infusions by study cut-off

- b. Total number of infusions per patient
- c. Number of IRs per total number of infusions
- 3. Protocol violations related to time SUA measured before pegloticase infusion
  - a. Number of times SUA was over 6
  - b. Number of patients who continued to receive infusion after SUA > 6 on 2 consecutive occasions in 24 and 52 week cohorts
  - c. Number of patients with premature (> 48 hours before infusion) SUA measures with AE, SAE (IRs, anaphylaxis).
- 4. Protocol violations related to dosing (schedule other than Q2 week dosing)
  - a. Number of patients with dosing violations with AE, SAE (IRs, anaphylaxis).
- 5. Number of patients in follow up
  - a. Reasons for loss to follow-up? (AEs, SAEs, death, etc.)
- 6. How would protocol be amended to encourage enrollment, study compliance, and significantly less number of completers (200) versus the original protocol (500)?

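### Section 3.5.6 lets a patient be taken off study for non-compliance or a protocol violation without keeping event collection open, so infusion reactions (IRs) on later commercial infusions could be missed and the IR proportion biased downward

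*Protocol*

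**What the plan says.** Protocol Section 3.5.6 lists the reasons for which a patient may be discontinued from the study. Two of them are "if they are non-compliant with study procedures, if there is a protocol violation". Every effort is then to be made to complete the Section 3.5.4 exit procedures, "preferably 4 weeks after their last dose of KRYSTEXXA but sooner if necessary". After that, only adverse events already ongoing, possibly or probably drug-related and of at least moderate severity are followed, for up to 30 days.

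Patients who stop the drug are treated differently. Under Sections 3.5.3 and 3.5.6 they "will be asked to remain in the study in follow-up for the remainder of their planned treatment duration". Section 3.5.4 is written for patients who do not agree to be followed for the year; they "are to return 4 weeks (+/- 5 days) after their final infusion of KRYSTEXXA".

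Section 3.4.1.2 states that "KRYSTEXXA is commercially available in the US", and under Section 3.3.2.1 starting it is a decision of patient and physician.

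For the analysis, Protocol Section 6.1.6 counts at most one event of each type per patient and tests whether "the rate of IRs seen in the Phase 3 studies will be reduced in this study by monitoring SUA prior to infusions". The SAP's Safety population is everyone with at least one full or partial infusion. Items 3 and 4 of the SAP's Report Format/Structure class as protocol violations matters of SUA timing, infusion after two consecutive values above 6, and dosing off the two-week schedule. Items 3c and 4a ask for adverse events, including IRs and anaphylaxis, in patients with premature SUA measurements or dosing violations.

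**The concern.** A patient who stops the drug has a route that keeps observation open. A patient removed for a violation does not. Nothing in Section 3.5.6 says that removal ends treatment, and the study does not control the supply. A willing patient who is removed while infusions continue fits neither Section 3.5.3 (drug stopped) nor the population described in Section 3.5.4 (consent to follow-up refused).

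The patients exposed to this rule may not be typical. Section 1.2.2 reports that most Phase 3 IRs occurred with uric acid above 6 mg/dL, as did every case meeting the anaphylaxis criteria except one at the first dose. Section 7.2.2 says that risk is higher once response is lost. Infusion after two high SUA values is one of the SAP's violations. Removal on that ground could therefore select patients at raised risk of the primary event.

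A removed patient stays in the denominator and can no longer enter the numerator. That lowers the reported proportion in the direction of the Section 6.1.6 hypothesis, and SAP items 3c and 4a could be incomplete. Section 6.1.5 expects considerable dropout but plans informative-dropout sensitivity analyses for efficacy endpoints only. None is stated for IRs.

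**Working it through.** **1. The plan's own figure.** Section 6.1.6 gives at least 90% power to distinguish 26% from 13% with at least 500 patients. Alpha, sidedness and the test are not stated. I assume a one-sample exact binomial test of p = 0.26 against a lower rate, one-sided 0.025, with 26% taken as fixed.
- n = 500: reject if at most 110 patients have an IR (110/500 = 22.0%). Exact size is 0.022 and power at 13% is above 0.999. At one-sided 0.05 the limit is 113 and power is again above 0.999.
- The stated floor is met; about 100 patients already give 90.6%.

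**2. Formula for the loss.** Let f be the share of dosed patients removed while still being infused and still IR-free. Let q be their risk of a first IR after removal, within the planned year. The denominator is unchanged, so

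reported rate = true rate − f × q.

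IRs before removal do not enter the loss term. The bias is downward whenever f × q > 0.

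**3. Inputs.** The documents give neither f nor q. I take f = 2%, 5%, 10% and 20%. For q I take 0.13 (the protocol's target rate), 0.26 (the Phase 3 rate) and 0.50 (an arbitrary high value). All are assumptions.

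**4. Bias in percentage points (f × q).**

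| f | q = 0.13 | q = 0.26 | q = 0.50 |
|---|---|---|---|
| 2% | 0.3 | 0.5 | 1.0 |
| 5% | 0.7 | 1.3 | 2.5 |
| 10% | 1.3 | 2.6 | 5.0 |
| 20% | 2.6 | 5.2 | 10.0 |

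**5. Chance of a false finding of reduction** if the true rate is still 26% (n = 500, rule from step 1; 2.2% with no loss).

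| f | q = 0.13 | q = 0.26 | q = 0.50 |
|---|---|---|---|
| 2% | 3% | 4% | 7% |
| 5% | 5% | 9% | 23% |
| 10% | 9% | 25% | 73% |
| 20% | 25% | 77% | about 100% |

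**6. How large f must be.** To move an expected 26% to the 22% limit by this route alone, f = (0.26 − 0.22)/q, which is 15% at q = 0.26 and 8% at q = 0.50. To imitate the whole fall to 13%, f = 0.13/q, which is 50% and 26%. If about 1,500 patients are dosed, the limit is 356/1,500 = 23.7%, and f falls to (0.26 − 0.2373)/0.26 = 8.7%, or 4.5% at q = 0.50.

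**7. If the true rate is 13%**, power is already above 0.999. The test conclusion is unaffected and only the estimate is too low.

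**The case against.** The case against is substantial and most of it stands as a limit on size and certainty.

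- Removal is permissive. Continued infusion after it is an inference that the text allows but does not state. The exit procedures are timed from the last dose, which assumes that dosing has ended.
- A reader might infer that IRs in patients treated outside the SUA rule go uncounted. The documents do not support that. A violation has to happen before anyone can be removed for it, so an IR on the violating infusion is seen on study; Section 1.2.2 puts 91% of Phase 3 IRs during the infusion itself. Violators stay in the Safety population, and the SAP plans to tabulate them. Only a first event on an infusion after removal can be lost.
- A reader might also infer that a patient removed while still being infused has no exit visit. Section 3.5.6 allows the procedures earlier than four weeks if needed, and the visit asks about adverse events since the previous one.
- The protocol tolerates some of the behaviour at issue. Section 3.5.5 says delayed or interrupted dosing need not lead to removal. Section 3.5.2.1 words the SUA rule both as a requirement and as advice, so the protocol itself does not clearly make infusion beyond it a violation, although the SAP lists it as one.
- The removal share is unknown, and 26% is the Phase 3 rate in all patients on the two-weekly regimen, not a measured risk in violators.

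These points do not close the gap. The two grounds are undefined, no sentence keeps event collection open after removal, follow-up then covers only events already ongoing, and no IR sensitivity analysis would show the effect.

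**Conclusion.** The point holds as a possible bias, not a demonstrated one. Section 3.5.6 permits outcome-related censoring of the primary safety endpoints. If patients are removed on these two grounds while commercial infusions continue, the IR proportion is understated by f × q. That is 0.3 to 1.0 points at f = 2% and 1.3 to 5.0 points at f = 10%, for assumed q of 0.13 to 0.50. At small f the effect is minor. A misleading test result needs a sizeable group removed IR-free and still infused: with 500 patients and a true rate of 26%, about 15% at q = 0.26 or 8% at q = 0.50 brings the expected rate to the rejection limit. The direction follows from the plan's own counting rule; the size cannot be fixed from the documents. The rule is still worth changing, because it touches the primary objective and costs little to repair.

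Section 3.5.6 also contradicts itself on a related matter. It names treatment discontinuation for SUA above 6 mg/dL as a ground for leaving the study, then says such patients will be asked to remain in follow-up. The two statements must be reconciled.

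**What to change.** - **Section 3.5.6:** remove non-compliance and protocol violation as grounds for ending study observation, and record them as deviations. Ask these patients to stay under observation. If they consent, collect infusion dates, IRs, anaphylaxis and immune complex-related events through the planned year. The change is limited to these two grounds, and treatment decisions are unaffected.
- **Same section:** reconcile the two statements on patients whose treatment stops for SUA above 6 mg/dL.
- **SAP reporting:** list any removals by reason, with the number of infusions received and the last SUA.
- **SAP analysis:** add an IR sensitivity analysis for patients who leave early. For example, assign those who left IR-free a range of later risks, such as 0.13, 0.26 and 0.50, and show how the proportion and its exact 95% interval move against 26%. Where it is unknown whether infusions continued, counting all such patients gives the upper bound on f.

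The cost is a wording amendment with IRB approval and a few added SAP tables. Collection can use visits already planned, and no patients are added. Some deviating patients may not attend, so the gap would narrow rather than close. The reported IR rate may be slightly less favourable.

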### **3.5.7 Gout flare Prophylaxis and Treatment**

#### **3.5.7.1 Gout flare Prophylaxis**

All patients should receive prophylactic treatment to reduce the risk of acute gout flares, unless medically contraindicated or not tolerated as noted in the FDA-approved KRYSTEXXA Full

Prescribing Information. The patient should begin a regime of colchicine or NSAID prophylaxis at least 1 week before the first dose of KRYSTEXXA and it should continue for at least 6 months after initiation of KRYSTEXXA therapy.

### **3.5.7.2 Gout flare Treatment**

An increase in gout flares is frequently observed upon initiation of anti-hyperuricemic therapy, including treatment with KRYSTEXXA. **Patients are to be instructed to contact the site within 12 hours from the onset of symptoms. Gout flares should be confirmed through questioning or direct observation.** It is recommended that all patients who experience a gout flare during the study should receive an anti-inflammatory treatment (e.g., NSAIDS, colchicine, corticosteroids) as clinically deemed indicated by the treating physician.

### **3.5.8 Infusion Reactions**

An IR will be defined as any AE or cluster of AEs, not attributable to another cause, that occurs during or within 2 hours after the infusion of KRYSTEXXA. Other cases that occur outside of the 2-hour window may also be categorized as an IR as per investigator discretion. Signs and symptoms of the event, and treatments administered, must be documented in the medical record and in the CRF/eCRF. Examples of events not considered as possible IRs include laboratory abnormalities that are unlikely to have occurred during or within 2 hours following the infusion (e.g., anemia, hypercholesterolemia), gout flares, most infectious diseases, or the recurrence or worsening of a known chronic medical problem identified in the patient's medical history.

#### **3.5.8.1 Infusion Reaction Prophylaxis**

Infusion reactions are not uncommon when biological agents are administered by i.v. infusion. Therefore, all patients will receive pre-treatment prophylaxis consisting of at least an antihistamine and corticosteroid prior to each infusion of KRYSTEXXA. In order to standardize this regimen, patients will use 60 mg fexofenadine po the night before and the morning of the infusion and 200 mg hydrocortisone iv before the infusion. If the investigator feels this regimen is not appropriate for an individual patient, s/he should contact the medical monitor to discuss alternative therapy. The name, dose and time of administration of each prophylactic medication will be recorded in the medical record and in the CRF/eCRF.

#### **3.5.8.2 Anaphylaxis**

For this study, anaphylaxis, an allergic reaction that is rapid in onset, can be serious, and may cause death, will be defined using the NIAID/FANN diagnostic clinical criteria (Sampson et al, 2006) as described in Table 1 below. This constellation of signs and symptoms will be documented in the medical record and in the designated CRF/eCRF page. All IRs, whether described as anaphylaxis or not, will be adjudicated for anaphylaxis based on the criteria below (refer to Section 3.9).

**Table 1 NIAID/FANN Clinical Criteria for Diagnosing Anaphylaxis**

Anaphylaxis is highly likely when the following criteria are fulfilled:
Acute onset of an illness (minutes to several hours) with involvement of the skin, mucosal tissue, or both (e.g., generalized hives; pruritus or flushing; swollen lips, tongue, or uvula)
AND AT LEAST ONE OF THE FOLLOWING:
a. Respiratory compromise (e.g., dyspnea, wheeze-bronchospasm, stridor, reduced peak expiratory flow, hypoxemia)
b. Reduced blood pressure (i.e., systolic blood pressure < 90 mm Hg or greater than 30% decrease from that person's baseline) or associated symptoms of end-organ failure (e.g., hypotonia [collapse], syncope, incontinence)

NIAID/FANN: National Institute of Allergy and Infectious Disease/Food Allergy and Anaphylaxis Network

